Study Schedule:	
Month Year of First-Participant-In (planned): August 2021 Month Year of Last-Participant-Out (planned): January 2024

Investigator(s):	
[name]. [name] (Sponsor-Investogator) Institution: UPD Bern Position: Chefarzt, Stv. Ärztlicher Direktor Address: [name] Mail: [contact]
 
Dr. phil. [name] (Sub-Investigator) Institution: UPD Bern Position: Psychologist Address: [name] Mail: [contact]

Study Centre(s):	
Single-centre Universitäre Psychiatrische Dienste Bern

Statistical Considerations:	
Our primary analysis will be a linear mixed model with the following co-variables: fixed intervention effect (TAU plus SleepExpert versus TAU plus sleep monitoring), fixed baseline ISI score effect, random patient effect (multiple ISI scores during follow-up), random cluster effect. Depending on model fit, we may need to simplify the model.

GCP Statement:	
This study will be conducted in compliance with the protocol, the current version of the Declaration of Helsinki, the ISO EN 14155 norm as well as all national legal and regulatory requirements.

ABBREVIATIONS

AE	Adverse Event
ASR	Annual Safety Report
BASEC	Business Administration System for Ethical Committees, (https://submissions.swissethics.ch/en/)
CA	Competent Authority (e.g. Swissmedic)
CEC	Competent Ethics Committee
CRF	Case Report Form
ClinO	Ordinance on Clinical Trials in Human Research (in German: KlinV, in French: OClin, in Italian: OSRUm)
eCRF	Electronic Case Report Form
CTCAE	Common terminology criteria for adverse events
DSUR	Development safety update report
GCP	Good Clinical Practice
IB	Investigator's Brochure
Ho	Null hypothesis
H1	Alternative hypothesis
HRA	Federal Act on Research involving Human Beings (in German: HFG, in French: LRH, in Italian: LRUm)
IMP	Investigational Medicinal Product
IIT	Investigator-initiated Trial
ICH	International Council for Harmonisation of Technical Requirements for Pharmaceuticals for Human use
ISO	International Organisation for Standardisation
ITT	Intention to treat
MD	Medical Device
MedDO	Medical Device Ordinance (in German: MepV, in French: ODim)
PI	Principal Investigator
SAE	Serious Adverse Event
SDV	Source Data Verification
SOP	Standard Operating Procedure
SPC	Summary of product characteristics
SUSAR	Suspected Unexpected Serious Adverse Reaction
TMF	Trial Master File

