6. STUDY DESIGN

6.1 General study design and justification of design

This project is a prospective randomized controlled clinical pilot trial with a cluster-crossover design

involving two groups: An interventional group (TAU, plus SleepExpert) and a control group (TAU plus sleep monitoring).

Two different wards in the trial site (UPD Bern) will constitute the clusters. The study is conceptualized with a crossover, i.e. clusters (wards) will first be randomized to one of the groups for a duration of 4 months. After a washout-phase of two months, they will then be allocated to the other group for another 4 months. The order (TAU plus SleepExpert first vs. TAU plus sleep monitoring first) will be randomly allocated in a 1:1 fashion.

A total of 60 patients will be included. Patients will be assessed before the intervention (T0) and at the following time-points after the start of the intervention: 1 week (T1), 2 weeks (T2), 12 weeks (T3) and 26 weeks (T4).

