7.3 Assignment to study groups

The two clusters (UPD wards) will be assigned to one of the following two study sequences – while one cluster will follow the first sequence, the other one will follow the second sequence. Which ward will follow which study sequence will be randomly assigned.

- TAU plus SleepExpert first for 4 months; fade-out for one month; wash-out for one month; TAU plus sleep monitoring for 4 months
- TAU plus sleep monitoring for 4 months; fade-out for one month, wash-out for one month; TAU plus SleepExpert for 4 months

During the TAU plus SleepExpert and TAU plus sleep monitoring phases, patients will be actively recruited. During the fade-out phases, no active recruitment will take place, but already recruited patients will be able to complete their treatment. During the wash-out phase, no recruitment and no study-related treatment will take place.

Depending at which stage of the study the ward stands at the time point when a subject is admitted to the ward, her or she will either receive TAU plus SleepExpert or TAU plus sleep monitoring, or, if admitted during the wash-out phase, the subject will not be able to participate in the trial.

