11.4.2 Primary Analysis

The primary outcome, i.e. the four overall scores of the ISI of all follow-up time-points will be analyzed with a mixed effects linear model. The model will take into account the hierarchical structure of the data: multiple ISI scores per patient and clusters (cross-over). Because of the complexity of the data and the small number of clusters we assume that we will not be able to introduce random effects for patients and clusters. However, our first approach will still be a linear mixed model with the following co-variables: fixed intervention effect (TAU plus SleepExpert versus TAU plus sleep monitoring), fixed baseline ISI score effect, random patient effect (multiple ISI scores during follow-up), random cluster effect. Depending on model fit, we may need to simplify the model and modify the random effects. This model is pre-specified and the rationale for switching will be made explicit. The analysis will be made after all data has been collected by one of the principal investigators.

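### The primary model has no period term for a two-ward, two-phase crossover, so a shift in ISI between the phases enters the treatment estimate unless the ward-by-phase numbers happen to balance

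*Combined protocol and SAP*

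**What the plan says.** **Design.** Section 6.1 has two wards, each allocated to one arm for four months. "After a washout-phase of two months, they will then be allocated to the other group for another 4 months" Section 7.3 splits the gap into one month of fade-out and one of wash-out, so the phases start 4 + 1 + 1 = 6 months apart. It assigns one ward to each order: "while one cluster will follow the first sequence, the other one will follow the second sequence". On numbers, section 6.1 says only "A total of 60 patients will be included"; there is no target or cap per ward or phase.

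**Model.** The synopsis states "Our primary analysis will be a linear mixed model with the following co-variables" and gives the same list as section 11.4.2: intervention, then "fixed baseline ISI score effect, random patient effect (multiple ISI scores during follow-up), random cluster effect". Neither place has a term for phase or for visit. Sections 11.4.1 and 11.4.2 mention the crossover in general words and attach no model term to it. Section 11.4.2 calls the model pre-specified.

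**Fallback.** The same section cites the few clusters and says "we assume that we will not be able to introduce random effects for patients and clusters". The remedy is: "Depending on model fit, we may need to simplify the model and modify the random effects". No order of simplification follows.

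**Objective.** Section 4.2 frames the primary objective as a group-by-timepoint interaction over six months. Section 11.4.3 applies the same procedure to BSI and BDI.

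**The concern.** In this design each ward supplies its own treatment-minus-control comparison, and that comparison is also one between phases. In the ward that starts with SleepExpert a phase shift counts against the intervention (or for it, depending on sign); in the other ward it works the opposite way. The two cancel only if both wards carry the same weight. A period term forces the cancellation; without it, cancellation depends on recruitment.

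Neither condition for a leak is far-fetched. Ward numbers follow admissions and consent, and sections 8.1.1 and 8.7 place no restriction on usual or later care, which can therefore drift. At stake is the preliminary efficacy estimate on which, under section 11.2, a confirmatory trial depends.

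Three smaller weaknesses sit in the same paragraph. A ward variance from two wards is barely estimable. Dropping the patient effect with nothing in its place would treat four scores from one person as independent. A model without visit terms does not match an objective worded as an interaction with time.

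**Working it through.** **Inputs from the documents:** 60 patients, two wards, two phases, one ward per sequence, ISI at T0 and four follow-ups. **Assumed, because the documents give no figure:** the shift π between phases (0.1 to 0.5 SD), its timing, the split of patients over ward and phase, an ISI correlation of 0.4 to 0.7, complete data. The plan states no figure on this point to reproduce.

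**1. The leak.** Let ward A have SleepExpert first, and let π be the phase-2 minus phase-1 shift. The within-ward treatment difference estimates τ − π in ward A and τ + π in ward B. Each has variance proportional to 1/w, with w = n1·n2/(n1+n2). A ward-adjusted model without period averages them with weights wA and wB:

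bias = π·(wB − wA)/(wA + wB)

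| Cells A1/A2, B1/B2 | wA | wB | Share of π |
|---|---|---|---|
| 15/15, 15/15 | 7.5 | 7.5 | 0 |
| 18/18, 12/12 | 9 | 6 | −1/5 |
| 20/20, 10/10 | 10 | 5 | −1/3 |
| 25/5, 15/15 | 4.17 | 7.5 | +0.29 |

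The last row has equal ward totals (30 and 30) and still leaks.

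**2. Does the treatment of ward matter?** At 20/20/10/10 the share is −0.333 with ward fixed, omitted, or random with an intraclass correlation up to 0.10. In 800 simulated REML fits with random ward (ICC 0.05) and no treatment effect, the mean estimate was −0.093 for π = 0.3 and −0.162 for π = 0.5. The ward variance was estimated as zero in about half of the fits.

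**3. Size.** ANCOVA on the mean of four follow-ups is equivalent to a random-intercept model with complete data. With ward fixed, no treatment effect, correlation 0.5 and the shift at all follow-ups but not at T0:

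| Shift (SD) | 2:1 wards: bias, type I error | 3:2 wards: bias, type I error |
|---|---|---|
| 0.2 | 0.07, about 7% | 0.04, about 5.5% |
| 0.3 | 0.10, about 8% | 0.06, about 6% |
| 0.5 | 0.17, about 14% | 0.10, 7 to 8% |

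With a period term, bias is within 0.003 SD and rejection about 5% throughout. With four equal cells there is no bias, but the unmodelled shift inflates the residual: at 0.5 SD the test rejects about 3%.

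A cruder check, with one score per patient and no baseline adjustment, gives 9.9% for 2:1 wards and 0.5 SD. The bias is the same, but the standard error is 0.258, against about 0.16 for four follow-ups with baseline.

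**4. Timing, at 2:1 wards and 0.5 SD.** A shift present at T0 as well as at all follow-ups: bias 0.05 to 0.10 SD, error 6 to 8%. T1 and T2 only: 0.08 SD, 7 to 8%. T0 to T2 only: about zero, 5%. A seasonal shift follows the calendar. An annual cosine of 0.5 SD at T0 is 0.496, 0.486, 0.062 and −0.500 at days 7, 14, 84 and 182, with mean (0.496 + 0.486 + 0.062 − 0.500)/4 = 0.136. After baseline adjustment at correlation 0.5 that is 0.136 − 0.25 = −0.114, and −0.114 × (−1/3) = +0.04 SD, opposite in sign to the cases above. Over correlations 0.4 to 0.7 simulation gives +0.02 to +0.08 SD and 5 to 8% error.

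**5. Price of the period term.** Its variance is (1/wA + 1/wB)/4, against 1/(wA + wB) without it. At 2:1: 0.0750 against 0.0667, ratio of standard errors 1.06. At 3:2: 0.0694 against 0.0667, ratio 1.02. With equal cells: 1.00.

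**6. Which contrast.** With T0 as a covariate, the intervention-by-visit test only asks whether the effect differs among T1 to T4. For a constant 0.65 SD benefit (equal cells, correlation 0.5) it rejects 5% of the time. A joint 4-df test of intervention and interaction has about 90% power, and the average effect about 98%.

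**7. What stays unidentified.** Intercept, ward, period and treatment use up all four cell means (rank 4, residual degrees of freedom 0).

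**The case against.** The strongest reply is that the size is assumed. The documents give no shift, split or correlation. Section 3.6 expects usual care to be comparable across groups, and most patterns examined leave the error at 5 to 8%, in a pilot that also collects qualitative experience. That stands as a limit on magnitude. It does not remove the gap, since nothing in the model protects the estimate if care or case mix does drift.

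Second, section 11.4 promises an SAP at the start of recruitment that fixes the models. A period term could be added there, so it would be wrong to infer that the plan rules one out. The fair statement is that no step named in this document removes the leak, while section 11.4.2 already calls its model pre-specified and offers only simplification.

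Four further inferences are tempting and do not hold:

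- *Random ward causes the leak.* The share is practically the same with ward random, fixed or omitted. Random ward is a separate weakness, which section 11.4.2 half-concedes.
- *Equal ward totals are safe, unequal totals are not.* The condition is on n1·n2/(n1+n2), as 25/5 with 15/15 shows.
- *Season would shift all follow-ups alike.* With phases six months apart and T4 at week 26, a seasonal shift has reversed by T4.
- *The objective requires a joint multi-degree-of-freedom test.* The objective is directional, a greater reduction, and the joint test is neither directional nor the more powerful choice here.

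**Conclusion.** The point holds. The pre-specified model lacks a period term in a design where treatment is estimated from ward-by-phase differences, and a phase shift leaks into the estimate unless n1·n2/(n1+n2) matches across wards. The leak shares are exact arithmetic. The bias and error rates rest on assumed shifts, splits and correlations. The 14% is a near-worst case (2:1 wards, 0.5 SD at every follow-up but not at baseline) and should not be read as the expected error; small shifts or near-balanced cells make the effect negligible. The direction of bias cannot be known in advance. The two-level random ward effect, the missing fallback order and the missing visit terms are real but separate, and are best cured in the same edit. This should be fixed before data are seen; it does not show that the trial's result will be biased.

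**What to change.** In section 11.4.2, the synopsis and the SAP, replace the list of model terms with:

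> Fixed effects for intervention, ward, period (first or second recruitment phase, by enrolment), baseline value of the outcome, visit (T1–T4) and intervention-by-visit; patient random intercept; no random ward effect; Kenward-Roger degrees of freedom. The primary contrast is the intervention difference averaged over T1–T4, given baseline. Per-visit differences and the intervention-by-visit test are supportive. If the model does not converge: ANCOVA on each patient's mean follow-up score with intervention, ward, period and baseline. Scores of one patient are never analysed as independent.

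Reword the objective in sections 4.2 and 11.1 and in the synopsis to match this contrast. Use the same structure for BSI and BDI, each with its own baseline and visits; section 5.2 and Table 1 differ on when the BSI is given, so settle that first.

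State the limit that this does not cure: with one ward per sequence no degrees of freedom remain for ward-by-period variance, and the p-values assume that it is zero.

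Cost: wording only. Ward and period take one degree of freedom each. If there is no shift, the standard error is unchanged with equal cells, about 2% larger with 3:2 wards and 6% larger with 2:1 wards.

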11.4.3 Secondary Analyses

Continuous outcomes (Brief Symptom Inventory, Beck Depression Inventory) will also be analyzed by a mixed effects linear model using the same procedure used to estimate the primary outcome. Binary outcome data will be analysed using mixed effect logistic regression with odds-ratio as the effect measure. The number of hospitalizations will be also analyzed by a mixed effects model. Interim analyses

No planned interim analysis

11.4.4 Safety analysis

The frequency of occurrence of adverse events of different categories will be analysed using descriptive statistics and compared between the two groups using Chi square tests.

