4.5 Safety Objectives

The study aims to assess short- and long-term safety of SleepExpert and its tolerability in terms of incidence of sleep- and mental-health related side effects and use of sleep medication.

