10.3.1 Foreseeable adverse events and anticipated adverse device effects

Potential adverse events are transitional worsening of the sleep disorder and / or the mental disorder, daytime tiredness and daytime sleepiness. No SAE that could be related to the investigational device or study procedures are expected during this clinical trial.

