11.2 Determination of Sample Size

A power analysis was conducted with G-Power (Faul, Erdfelder, Lang, & Buchner, 2007). Assuming an alpha error level of 0.05 (two-sided) and a power of 0.8, a total sample size of n=60 will be sufficient to detect a medium effect (Cohen's d=0.65). This is a pilot trial with the primary aim of collecting qualitative experience and preliminary efficacy data. A large confirmatory trial will be conducted if the results of this pilot trial are encouraging.

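### Adverse events are compared between arms only by chi-square tests, with no effect estimate or interval, so at about 30 patients per arm a non-significant result says little about safety unless events are common

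*Combined protocol and SAP*

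**What the plan says.** Protocol section 4.5 sets the aim: "The study aims to assess short- and long-term safety of SleepExpert and its tolerability", judged by how often sleep-related and mental-health-related side effects occur and by use of sleep medication. Section 10.3.1 names what might be seen: "Potential adverse events are transitional worsening of the sleep disorder and / or the mental disorder, daytime tiredness and daytime sleepiness". It gives no expected rates.

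The safety analysis in section 11.4.4 is one sentence. Adverse-event frequencies by category are to be "analysed using descriptive statistics and compared between the two groups using Chi square tests". It names no effect measure, interval, margin, continuity correction or exact test, and no rule for reading a non-significant result.

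On size, section 6.1 states: "A total of 60 patients will be included". Section 11.2 justifies that number for an effect of d = 0.65 only, with the condition "Assuming an alpha error level of 0.05 (two-sided) and a power of 0.8". No power or precision is given for safety. Section 11.4.3 does name an effect measure, the odds ratio, for binary data under the secondary analyses. Section 11.4.4 has no counterpart for adverse events.

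**The concern.** The side-effect part of the safety objective asks how much more often, if at all, side effects occur with SleepExpert. Per-arm frequencies plus a p-value do not answer that. Frequencies carry no uncertainty about the difference, and the p-value shows neither its size nor what excess the data leave open.

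In a trial of 60 patients this matters because non-significance is the likely result over a wide range of event rates even if SleepExpert doubles the risk. Section 2.2 describes the target group as the new aspect of the study, and section 11.2 foresees a large confirmatory trial if the pilot is encouraging. A bare report of no significant difference in adverse events would carry forward without the range of excess risk still compatible with the data.

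**Working it through.** **The plan's own figure.** There is none for safety. The only sample-size figure is n = 60 for d = 0.65. Two-sided, normal approximation: 2 × (1.960 + 0.842)² / 0.65² = 37.2, so 38 per arm and 76 in total (78 with the t-test). One-sided: 2 × (1.645 + 0.842)² / 0.65² = 29.3, so 30 per arm and 60 in total. The stated 60 therefore matches a one-sided test, not the two-sided one described. That is a separate matter. The calculations below take 60 patients as planned.

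**Inputs.**
- Total 60 (section 6.1).
- 30 per arm: an assumption. Two wards swap arms (section 7.3) and no quota per arm is stated.
- Two-sided 0.05: an assumption for these tests. The documents set it only for the sample size.
- Control-arm risk 5% to 40%, doubled under SleepExpert: an assumption, because no rate is given.
- Patients with at least one event, treated as independent.

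**Chance of missing a doubling.** Approximate power is Φ[(|p₂ − p₁| − 1.96·SE₀)/SE₁], with SE₀ = √(2p̄(1 − p̄)/n) and SE₁ = √((p₁(1 − p₁) + p₂(1 − p₂))/n). For 10% versus 20%: p̄ = 0.15, SE₀ = √(0.255/30) = 0.0922, SE₁ = √(0.25/30) = 0.0913. This gives (0.10 − 0.1807)/0.0913 = −0.884, so power is 0.188. Exact enumeration of the two binomials gives 0.194, a miss rate of 81%. Exact results for all pairs follow. The last column is the number per arm for 80% power.

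| Control to SleepExpert | Power, 30 per arm | Missed | Missed, Yates or Fisher | Missed, 24 per arm (uncorrected) | Needed per arm |
|---|---|---|---|---|---|
| 5% to 10% | 0.106 | 89% | 98% | 92% | 435 |
| 10% to 20% | 0.194 | 81% | 90% | 83% | 199 |
| 20% to 40% | 0.392 | 61% | 70% | 67% | 82 |
| 25% to 50% | 0.516 | 48% | 59% | 55% | 58 |
| 30% to 60% | 0.663 | 34% | 44% | 41% | 42 |
| 40% to 80% | 0.905 | 10% | 15% | 16% | 23 |

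The 24-per-arm column is a sensitivity case. Section 9.2.5 does not replace patients who withdraw after starting, and no dropout rate is given.

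**What an interval would show.** Take an observed doubling, 6/30 versus 3/30.
- Chi-square = 60 × (6 × 27 − 24 × 3)² / (30 × 30 × 9 × 51) = 486,000 / 413,100 = 1.18, p = 0.28.
- Wilson limits are 0.095 to 0.373 for 6/30 and 0.035 to 0.256 for 3/30.
- Newcombe lower limit: 0.10 − √((0.200 − 0.095)² + (0.256 − 0.100)²) = −0.09.
- Newcombe upper limit: 0.10 + √((0.373 − 0.200)² + (0.100 − 0.035)²) = 0.285, or +29 points.

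Equal counts, 3/30 versus 3/30, give 0 with limits of −17 to +17 points. With 0/30 events, the exact one-sided 95% upper bound is 1 − 0.05^(1/30) = 9.5%.

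**The case against.** The strongest reply is that safety does not rest on these tests alone. ISI, BSI and BDI are compared by mixed models that estimate an intervention effect, and they bear on worsening of sleep or mental state. Medication use and hospitalization are also between-arm outcomes, with odds ratios planned for binary data. Adverse events are classified by severity and relatedness. All of this stands. A reader might infer that chi-square tests are the only safety comparison, or that nothing else could inform a safety conclusion. The documents do not support either inference. But mean differences do not replace counts of patients harmed, and the adverse-event comparison itself still has no estimate.

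A reader might also infer that the plan treats p > 0.05 as proof of safety. It does not say so. That misreading is a risk the current wording leaves open.

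The miss rates depend on the assumed control risk. Events are asked about at five time points up to 26 weeks, so common categories cannot be ruled out, and for those the test does much better (10% missed at 40% to 80%). This also stands. It limits the claim to events that are not common.

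Nor do the documents show that ward clustering makes matters worse. Each ward contributes to both arms, so stable ward differences largely cancel. No such claim is made here.

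Finally, this is a pilot, section 11.4 promises a separate SAP, and low power at 60 patients cannot be removed by wording. The pilot status argues for estimation rather than testing. The later SAP could add intervals, but the method committed to in section 11.4.4 is the chi-square test.

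**Conclusion.** The point holds for the comparison of adverse events. As written, section 11.4.4 yields frequencies and p-values but no measure of the difference or its uncertainty. With an assumed 30 independent patients per arm and two-sided 0.05, a true doubling is missed more often than not for control risks up to 20%, in about half of trials at 25%, and in about a third at 30%. A non-significant result is therefore weak evidence on the section 4.5 objective unless events are common. This is a cheap improvement to the analysis and reporting. It is not a finding that SleepExpert is unsafe or that the trial's design fails.

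**What to change.** In section 11.4.4, make estimation the main adverse-event comparison:

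- For each category, and for patients with at least one event, report the number of patients per arm and the risk difference (SleepExpert minus monitoring) with a 95% Newcombe interval, labelled as unadjusted for ward and period.
- When an arm has zero events, add an exact upper bound for that arm.
- Keep any p-value as descriptive only.
- State that the safety conclusion rests on the interval, that p > 0.05 will not be reported as absence of harm, and that the pilot can exclude only large excesses.

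Cost: a few sentences in the protocol or SAP and a few more table columns, with no extra data or patients. The drawback is a less favourable safety statement, because the intervals will be wide.

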6.2.3 Other methods of minimising bias

- The primary applicant is a staff member at the sleep clinic of the University Psychiatric Services Bern. The resources at this established, specialized sleep clinic will ensure that included patients are carefully diagnosed, i.e. that only patients fulfilling the defined eligibility criteria will be included. This ensures generalizability of the results to the intended population.
- Study attrition and reasons for dropout will be carefully documented throughout the study period.
- An intention to treat analysis will be provided since a per-protocol analysis may result in biased effects if many patients drop out due to (perceived) inefficacy.
- The outcome measures are widely used, valid, and reliable measures that have been recommended by experts for the research assessment of insomnia (Buysse, Ancoli-Israel, Edinger, Lichstein, & Morin, 2006).
- Therapists will be experienced, well-trained, and supervised.
- The trial will be registered in a publicly accessible database before recruitment of the first subject. Hypotheses and the analysis plan will be made publicly available. This precludes that the analysis plan is changed after inspection of the data ("fishing for significances").

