7.4 Criteria for withdrawal / discontinuation of participants

Participants will be withdrawn from the study immediately if there are any concerns about the participants' safety. Participants can also choose to withdraw from the study at any time, and are not required to provide their reason for withdrawing from the study. Coded data acquired before withdrawal will be analyzed.

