8.5 Data Collection and Follow-up for withdrawn participants

If a patient withdraws consent for further study participation, the data collected up to the time point of withdrawal will be included in the study and no further data will be collected. The data of withdrawn participants will not be anonymized but will remain coded after analysis of the data set.

For participants who discontinue the study intervention but do not withdraw from participation in the study, study visits and data collection will continue in the same way as for non-withdrawn participants.

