9.2.5 Assessments in participants who prematurely stop the study

For participants who discontinue the study intervention but do not withdraw from participation in the study, study visits and data collection will continue in the same way as for non-withdrawn participants.

Dropouts before start of treatment (i.e. non-starters) will be replaced by recruitment of new participants.

Patients who started the intervention but who were prematurely withdrawn from the study will not be replaced by newly enrolled patients.

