10.3 Medical Device Category A studies

Device deficiencies and all **adverse events (AE)** including all **serious adverse events (SAE)** are collected, fully investigated, and documented in the source document and appropriate case report form (CRF) during the entire study period, i.e. from patient's informed consent until the last protocol-specific procedure. Documentation includes dates of event, treatment, resolution, assessment of seriousness, and causal relationship to device and/or study procedure [ISO 14155, 6.4.1.].

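### Adverse events are compared by chi-square without regard to follow-up time, so unequal loss from the study would bias the comparison of later events in favour of the arm that loses more patients

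*Combined protocol and SAP*

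**What the plan says.** The whole safety analysis in 11.4.4 is one sentence: event counts by category are to be summarised descriptively, then "compared between the two groups using Chi square tests". It names no person-time denominator, incidence rate, censoring rule or table of follow-up.

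Section 8.5 deals with two groups differently. After withdrawal of consent, "the data collected up to the time point of withdrawal will be included in the study and no further data will be collected". For patients who stop the intervention but remain in the study, "study visits and data collection will continue in the same way as for non-withdrawn participants". Section 7.4 adds that participants are "withdrawn from the study immediately if there are any concerns" about their safety.

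Events are asked about at T0, T1, T2, T3 and T4 (9.2.4.1), that is, up to day 182. Section 10.3 requires onset information: "Documentation includes dates of event, treatment, resolution, assessment of seriousness, and causal relationship to device and/or study procedure". Section 6.2.3 undertakes to document attrition and its reasons. The safety objective in 4.5 covers both the short and the long term.

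**The concern.** A test on frequencies gives a patient seen for 14 days the same weight in the denominator as one seen for 182 days. The first patient is in effect counted as event-free for 24 weeks in which nobody asked. If both arms lose patients equally and have the same risk, this does no harm to the comparison. If they lose patients unequally, the arm with more loss looks safer than it is.

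Unequal loss is possible here. Inpatient stays are typically one to eight weeks (8.1.1), so the week-12 and week-26 assessments usually fall after discharge. The arms also differ in what they ask of patients and use different information sheets (6.2.2). What is at stake is the long-term part of the safety objective, because most of the observation time lies after T2.

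**Working it through.** **Plan's own figure.** None exists. The documents give no adverse-event rate, no dropout rate and no power for the safety comparison. All rates below are therefore assumptions. I read frequency as the proportion of patients with at least one event.

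**Time observed.** T2 is day 14 and T4 is day 182 (Table 1). A patient leaving at T2 is observed for 14/182 = 7.7% of the planned time, and 168 of the 182 days lie after T2.

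**Model.** Let p be the true 26-week risk, with constant weekly rate λ = −ln(1 − p)/26. Let a fraction L leave the study at week 2. Then

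observed proportion = (1 − L)·p + L·(1 − e^(−2λ)).

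**Equal true risk, p = 0.40.** λ = 0.5108/26 = 0.01965, and the two-week risk is 1 − e^(−0.0393) = 0.0385.
- L = 0.30: 0.70 × 0.40 + 0.30 × 0.0385 = 0.292.
- L = 0.10: 0.90 × 0.40 + 0.10 × 0.0385 = 0.364.

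The gap is 7.2 points with no true difference. Swapping the two dropout fractions swaps the two proportions, so the sign of the bias follows the dropout. With equal fractions the gap is zero.

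**The same case by person-time.** Expected time at risk to first event is the observed proportion divided by λ: 0.292/0.01965 = 14.8 weeks and 0.364/0.01965 = 18.5 weeks per patient. Events divided by time give 0.0196 per person-week in both arms, so the spurious gap disappears.

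**A true excess in the arm with more loss.** Take a true hazard ratio of 2, control risk 20%, about 30 patients per arm (assumed from the total of 60), and week-2 exit.

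| Leaving (higher-risk arm v other) | Observed risks | Risk ratio | Chi-square power | Rate ratio |
|---|---|---|---|---|
| none | 36.0% v 20.0% | 1.80 | 28% | 2.00 |
| 30% v 10% | 26.2% v 18.2% | 1.44 | 11% | 2.00 |

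With 30% v 10% leaving, a person-time comparison has about 24% power (24.3% by the Schoenfeld formula; 24.1% for a simulated log-rank test, against 10.7% for the simulated chi-square).

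**How much loss hides the excess completely.** Over control risks of 10% to 50%, erasing a hazard ratio of 2 needs about 39–52% lost by week 2 from the higher-risk arm with no loss from the other, or 45–57% with 10% lost from the other. For a hazard ratio of 1.5 the ranges are about 26–34% and 34–41%.

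**Early events only.** If all events fall in weeks 0–2 (20% v 36%) and patients leave at week 2, the risk ratio stays at 1.80. If they leave at week 1, 30% v 10%, it falls only to 1.64.

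**The case against.** A reader might infer that dropout will be heavier on SleepExpert, so that the planned test would hide a real harm of the programme. The documents do not support that.
- The remark on attrition in 6.2.3 is conditional, "if many patients drop out due to (perceived) inefficacy", names no arm, and serves to justify an intention-to-treat analysis. Perceived inefficacy could apply at least as well to a monitoring app that gives no advice. Heavier loss from control would overstate harm on SleepExpert.
- Finding the programme demanding and stopping it does not shorten observation, because 8.5 and 9.2.5 keep such patients in follow-up. Only study withdrawal or loss to follow-up matters.
- The foreseeable effects in 10.3.1 are transitional worsening, tiredness and sleepiness. T1 and T2 would catch most of these before a week-2 exit.

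A reader might also blame the rule that "Patients who started the intervention but who were prematurely withdrawn from the study will not be replaced by newly enrolled patients". That lowers numbers but does not create the bias; unequal follow-up does.

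Two further objections concern size. With about 30 per arm, a 7-point gap is roughly two patients, and the 95% half-width for a difference between 29.2% and 36.4% is about 24 points. Power is also low with complete follow-up. Finally, 11.4 defers detail to a separate SAP that may already cover exposure.

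These objections stand as limits on direction and size. They leave the defect in place: the comparison as written has no protection against unequal follow-up. Multiple imputation (11.5) is not tied to adverse events.

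**Conclusion.** The point holds in conditional form. If study withdrawal or loss to follow-up differs between arms, the 11.4.4 comparison of later events is biased in favour of the arm with more loss, whichever arm that is. In the illustration the bias is about 7 points (29.2% v 36.4% under a common true risk of 40%). This rests on a constant event rate and on 30% v 10% leaving at week 2, none of which comes from the documents. The effect is small or absent for transient events that occur before patients leave.

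It would go too far to say that the safety objective will be answered wrongly. In a pilot of 60, a non-significant chi-square would not establish safety even with full follow-up. This is a worthwhile, inexpensive improvement to the long-term safety comparison.

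**What to change.** In 11.4.4, report by arm the person-weeks observed and the adverse-event incidence rate per person-week. Use the rate ratio or rate difference with 95% CI as the between-group comparison, in place of relying on the chi-square p-value. Show events by visit window (to T2, T2–T3, T3–T4) with the number still under observation in each. Tabulate study withdrawals and their reasons by arm, with safety withdrawals shown separately.

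Time to first event, censored at last contact, can be a supportive analysis. It should not be the main one: there are only about 60 patients, and onset dates may have to be recalled across gaps of 70 days (T2–T3) and 98 days (T3–T4).

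The cost is SAP wording and slightly more analysis. Event dates (10.3) and attrition (6.2.3) are already to be recorded, so no new data or visits are needed. One limitation remains: rates are still biased if withdrawal is related to harm, which the safety withdrawals in 7.4 make possible. The plan should therefore describe the comparison as descriptive.
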